5. BACKGROUND

Endometrial cancer is a surgically staged disease. Staging involves removal of the uterus, tubes and ovaries as well as lymph nodes in the pelvic and aortic regions. In women with cancer that does not invade the uterine muscle or is of low grade and invades less than 50% of the muscle, removal of the lymph nodes is not mandatory. Intraoperative evaluation of the depth of invasion of the cancer is critical, therefore, in determining which patients require lymphadenectomy. Gross visualization is highly inaccurate. It is more sensitive to obtain a pathological frozen section on the uterus to accurately diagnose depth of invasion. However, frozen section increases the operative time and incurs an additional expense for the procedure. A rapid and accurate intraoperative assessment of invasion which could be performed in the operating room would reduce the time and expense of a frozen section. We propose to utilize fluorescein dye given intravenously prior to the hysterectomy to aid in visually determining the depth of invasion. If this assessment correlates well with the pathologic depth of invasion, then this could represent a valuable intraoperative tool to determine which patients require lymphadenectomy.

Fluorescein is approved by the FDA for angiography of the retinal vessels. There are many procedures that utilize fluorescein beyond its FDA indication. It is commonly used during surgery to assess the vascular viability of tissue, most particularly the viability of the intestines when there is concern. In this situation, fluorescein is injected intravenously and the intestines are examined using a Woods lamp to detect the areas of fluorescence. Areas of poor vascularity will not fluoresce. It is also commonly used to detect the boundaries of skin lesions. For example, in assessment of vulvar Paget's disease fluorescein injection and visualization of the vulva with Woods lamp can detect the extent of the lesion that would otherwise not be detectable by the naked eye.

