6. TRIAL OBJECTIVES

- a. **Primary Objective:** To determine if Fluorescein systemic injection during hysterectomy procedure can be useful in revealing the depth of endometrial cancer invasion
- b. **Secondary Objectives:** To compare depth of invasion as detected with fluorescein to that detected by frozen section and final pathology
- c. **Exploratory Objectives:** Can systemic fluorescein injection at time of hysterectomy provide an inexpensive and rapid determination of endometrial cancer invasion into the myometrium

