9. TREATMENT PLAN

a. On-Study Evaluation:

After signing the IRB-approved informed consent form, research participants will be registered by a clinical research associate (CRA) in the Cancer Clinical Trials Office (CCTO). Upon registration, surgery will be scheduled at the next available surgery time slot. All research participants will receive fluorescein injection through their existing intravenous line during their operative procedure for endometrial cancer staging. This will consist of one ampule (5 cc) injected intravenously prior to ligation of the uterine arteries. After the uterus is removed it will be sent to surgical pathology for evaluation as per routine care. The pathologist will open the uterus and evaluate the endometrium. He or she will then cut into the myometrium in an area most suspicious for invasion. The cross section of the myometrium and endometrium will be photographed while exposed to a Woods lamp. The normal myometrium will have a yellow fluorescent appearance under the Woods lamp. The cancerous tissue will have minimal fluorescence. The measurement will be taken estimating the depth of invasion of the cancer into the myometrium on the basis of its physical appearance under the Woods lamp. Cross-sectioning of the uterus is routine procedure by pathology for the intra-operative evaluation of endometrial cancer. This information routinely is provided in order to determine if lymph node staging is necessary.

The area that was measured and photographed will then be prepared for a frozen section to document depth of invasion. This is the standard procedure performed during an endometrial staging. The depth of invasion on the frozen section will be recorded. This same area will undergo histologic confirmation by permanent pathology to determine depth of invasion. The frozen section is part of routine standard of care in evaluation of endometrial cancer.

Subjects will be informed prior to participation in this study that they will have a bright yellow discoloration of their urine and possibly a mild yellow discoloration of their skin for up to 24 hours after the procedure.

b. Dose Assignment: This is a single arm study. A single dose of Fluorescein will be administered to all subjects in this study.

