14. STATISTICAL CONSIDERATIONS

- a. Sample Size and Study Duration:** 100 subjects will be entered into this pilot study. It is estimated that this study will be completed in less than one year.

- b. Study Endpoints:** Invasion depth as determined using each of three methods: Systemic Fluorescein Injection (SFI), Frozen Section (FS), and Permanent Section (PS).
- c. Data Analysis Plan:** The primary objective is basically to determine whether the SFI method works. Provided that it works, the analysis plan in support of the Secondary Objective is as follows: For each study subject, the paired difference in invasion depths determined using the SFI versus FS methods will be calculated and expressed as a percentage of the FS-based invasion depth. Likewise, the paired difference in invasion depths determined using the SFI versus PS methods will be calculated and expressed as a percentage of the PS-based invasion depth. Each type of paired difference will be summarized as the mean and standard deviation. Because PS is considered the definitive “gold standard” of determining invasion depth, the mean of the paired differences between SFI and PS methods will be compared against equivalence limits of -25% and $+25\%$ via the Two One-Sided Tests (TOST) procedure using an $\alpha=0.10$ significance level. If this mean is significantly “in between” both equivalence limits, then this will indicate that the discrepancy in invasion depths between SFI and PS is significantly less than 25% , and we will accordingly consider further investigation of the SFI method of determining invasion depth.

Sample Size and Power: When two methods are equivalent, the mean of their paired difference will be 0% . The power of the TOST procedure to declare that a mean of 0% is significantly “in between” equivalence limits of -25% and $+25\%$ depends heavily on the standard deviation of the paired difference when the sample size is fixed at 20 subjects. A simulation study using 1,000,000 simulations in PASS 12 software indicates that 20 subjects gives the TOST procedure $>90\%$ power at 10% alpha to declare a mean of 0% to be significantly “in between” the above-stated equivalence limits provided that the standard deviation of the paired differences is less than 37% . This power calculation shows that, if SFI agrees well with PS, then 20 subjects should provide our study with sufficient power to demonstrate that fact.

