- d. Missing, Unused and Spurious Data:** Missing data will be treated as missing, and will not be imputed. Spurious data will be corrected at the source document. Any data documented as spurious that is unable to be corrected at the source will be treated as missing.

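### The primary objective has no criterion yet decides whether the only formal test is run, and that test concerns a mean but is worded as agreement; failed readings and the 50% cut-off are not covered.

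*Combined protocol and SAP*

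**What the plan says.** Section 6 sets the primary objective as whether systemic fluorescein "can be useful in revealing the depth of endometrial cancer invasion". Section 14c restates it and makes the rest conditional: "The primary objective is basically to determine whether the SFI method works. Provided that it works". What follows is described as serving the secondary objective. Section 14b lists invasion depth by three methods (SFI, frozen section FS, and PS) as endpoints, but ties none of them to the primary objective.

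For each woman the SFI-FS and SFI-PS differences are expressed as a percentage of the FS or PS depth. "Each type of paired difference will be summarized as the mean and standard deviation". For the one formal test, "the mean of the paired differences between SFI and PS methods will be compared against equivalence limits" of ±25% at alpha 0.10. If the mean lies significantly between the limits, "this will indicate that the discrepancy in invasion depths between SFI and PS is significantly less than" 25%, and further investigation of SFI will be considered.

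Section 14d adds: "Missing data will be treated as missing, and will not be imputed". Section 9a has the pathologist estimate SFI depth from appearance under the Woods lamp. It then sends the measured area to frozen section, and: "This same area will undergo histologic confirmation by permanent pathology to determine depth of invasion".

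The Background (section 5) explains why depth matters. Lymph node removal is described as not mandatory "In women with cancer that does not invade the uterine muscle or is of low grade and invades less than 50% of the muscle".

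**The concern.** Three gaps combine.

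- **No criterion.** Neither *useful* nor *works* has a measure, a threshold or an analysis. Two analysts with the same data could disagree on whether the primary objective was met and on whether the TOST should be run.
- **Failed readings.** The documents do not mention a specimen with no readable boundary. If it is recorded as missing, section 14d leaves it out of the paired differences and nothing counts it against SFI. If it is recorded as depth 0 in a woman with invasion, it enters as -100%. The two conventions push the result in opposite directions.
- **Mean read as agreement.** Over- and under-estimates cancel in a mean, so a pass does not show that individual women agree within 25%. The SD will be reported, but no criterion applies to it, and it does not show how many women change sides at the 50% cut-off.

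At stake is a pilot that follows its plan exactly and still supports an overstated conclusion about SFI.

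**Working it through.** **Inputs from section 14:** limits ±25%, alpha 0.10 per one-sided test, true mean 0%, SD below 37%, power above 90% with 20 subjects, and 100 subjects to be entered. **Assumed, because the documents give no figures:** normal differences, readable rates and depth distributions.

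**1. The plan's own figure.** The TOST passes if |mean| + t(0.90, n-1) × s/√n < 25. With true mean 0, power is the average of 2Φ[(25 - t·s/√n)/(σ/√n)] - 1 over the distribution of s, where (n-1)s²/σ² is chi-square on n-1 df and the term is 0 when t·s/√n exceeds 25. For n = 20 and σ = 37, t = 1.328 and power is 90.6%. A simulation gives 90.5%. The normal approximation gives 2Φ(25/8.273 - 1.282) - 1 = 91.8%, where 8.273 = 37/√20. The stated figure of above 90% is reproduced.

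**2. Mean versus individual women.** The share of women differing from PS by more than 25% is 2[1 - Φ(25/SD)].

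| SD | Share beyond 25% | TOST power, 20 pairs | TOST power, 100 pairs |
|---|---|---|---|
| 37% | 2[1 - Φ(0.676)] = 50% | 90.6% | over 99.9% |
| 60% | 2[1 - Φ(0.417)] = 68% | 41% | 99.6% |

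The 37% is the ceiling in the plan's power statement, not an expected value. Normality is strained at 60%: it puts 4.8% of differences below -100%, which is impossible.

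**3. Unreadable specimens recorded as missing** (SD 37%). Section 14 gives both 100 and 20 subjects, so both are shown.

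| Readable rate (assumed) | Pairs of 100 | Power | Pairs of 20 | Power |
|---|---|---|---|---|
| 80% | 80 | above 99.99% | 16 | 82% |
| 60% | 60 | 99.99% | 12 | 67% |
| 40% | 40 | 99.7% | 8 | 40% |

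With 100 women the test hardly reacts to the readable rate. With 20 it does, but only through lost pairs. By contrast, 100 women would estimate the rate directly: 80/100, 60/100 and 40/100 have exact 95% CIs of 71-87%, 50-70% and 30-50%.

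**4. Unreadable specimens recorded as depth 0.** If each woman has a 30% chance of a -100% entry and the rest have mean 0 and SD 37%, the expected mean is 0.30 × (-100) = -30%, outside the limits. The TOST then passes about 5% of the time with 20 women and 1.5% with 100. The recording convention can therefore decide the outcome.

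**5. The 50% cut-off.** Take SFI = PS × (1 + error), error SD 0.37, no zero depths, and three assumed distributions of depth as a fraction of myometrial thickness. Deep tumours called shallow per 100 women are 10.9 (uniform), 7.7 (Beta(1.2, 2.2)) and 4.0 (Beta(1, 3)). Shallow tumours called deep are about 5-7 per 100. Nothing in the plan would display either count.

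**The case against.** The strongest reply is that the condition in section 14c is itself the place where method failure could stop the sequence, so poor readability need not reach the TOST. That is possible. But a condition without a definition is not a safeguard, because it can be judged met at any readable rate.

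A reader might infer that the go rule is blind to failed readings, or that the TOST passes almost regardless of spread. The documents do not support either in general. Both hold only if about 100 pairs are analysed, and the first also needs failures to be recorded as missing. With 20 women, power falls to 82%, 67% and 40% as readability falls, and at SD 60% it is only 41%. That failures drop out is itself an inference: section 9a would also allow a depth of 0 to be recorded.

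It is also fair that section 14c names the mean in the clause leading to its conclusion, reports the SD, and promises only to consider further investigation. Frozen section remains standard care, and no passage lets SFI guide surgery. These facts limit the consequences. They do not correct the conclusion drawn, which is about the discrepancy and not its mean.

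Finally, a readable rate alone would not answer the primary objective, since a clear boundary can lie at the wrong depth. That stands, and the fix pairs readability with agreement.

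**Conclusion.** The point holds and should be addressed. The primary objective has no measure or criterion, yet the only formal test depends on it. The recording of unreadable specimens is unspecified and can change the result. A pass supports only a mean within 25% among the pairs analysed: at SD 37% and mean 0, it coexists with half of the women beyond 25%. The cut-off that gives depth its stated purpose is not analysed; under the assumed distributions at SD 37%, about 4-11 deep tumours per 100 would be called shallow.

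The text points in section 14 are certain. The sizes rest on normal differences, a zero mean, assumed readable rates and depth distributions, and on whether 20 or 100 women are analysed. A reader might also infer that the trial has no endpoints or that its power figure is wrong. Neither is so: section 14b lists depth by three methods, and the power figure reproduces.

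**What to change.** 1. Record SFI as readable yes/no, separately from a depth of 0. Report the readable rate over all women who receive fluorescein and have the uterus examined, with an exact 95% CI. Make this the feasibility part of the primary objective, alongside agreement with PS depth. The sponsor sets any go threshold in advance, and the go rule considers the readable rate together with the TOST.
2. Delete the opening condition in section 14c, so that the depth comparison is always reported.
3. Word the TOST conclusion as applying to the mean percent difference among readable pairs with PS depth above 0. For women with PS or FS depth 0, where the percent difference is undefined, report their number and the absolute difference.
4. Add a descriptive cross-classification (below 50% versus 50% or more of myometrial thickness) of SFI against same-area PS, with sensitivity, specificity and exact 95% CIs. Show it with unreadable cases counted as incorrect and again among readable cases only. Label it as the depth call alone, since SFI does not measure grade. Capture percent depth or thickness for each method if the CRF does not already do so.

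**Cost:** protocol wording, one yes/no field and possibly one value per method; no extra subjects or procedures. The figures will look less favourable when unreadable cases count as incorrect. Intervals will be wide and depend on the unknown number of deep tumours. About 13 deep per 100 with 4 missed (near the Beta(1, 3) case) gives sensitivity 9/13, exact 95% CI 39-91%. Fifty deep with 11 missed (the uniform case) gives 39/50, 64-88%.

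### Section 14c tests only the pooled mean of signed percent differences, so a fluorescein reading whose bias changes with depth can pass as equivalent

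*Combined protocol and SAP*

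**What the plan says.** Section 14c (Data Analysis Plan) forms a signed difference for each woman. For the comparison with permanent section it "will be calculated and expressed as a percentage of the PS-based invasion depth". The planned summary is short: "Each type of paired difference will be summarized as the mean and standard deviation". For the formal test, "the mean of the paired differences between SFI and PS methods will be compared against equivalence limits of" −25% and +25%, by TOST at α = 0.10. A pass is taken to mean that the discrepancy in invasion depth between SFI and PS is significantly below 25%, and further investigation of SFI is then considered.

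The power text starts from "When two methods are equivalent, the mean of their paired difference will be 0" percent. It states that "20 subjects gives the TOST procedure" more than 90% "power at 10% alpha to declare a mean of 0% to be significantly" inside the limits, "provided that the standard deviation of the paired differences is less than 37" percent. Section 14a enrols 100 women.

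Section 5 (Background) sets the standard for SFI: "If this assessment correlates well with the pathologic depth of invasion", it could become an intraoperative tool for deciding who needs lymphadenectomy. Section 7 does not restrict eligibility by depth, so shallow and deep tumours are pooled. No section plans a slope, an analysis by depth, an absolute error or limits of agreement.

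**The concern.** A mean of signed errors measures average bias only. If SFI reads shallow tumours too deep and deep tumours too shallow, the percentages have opposite signs and the pooled mean can sit near 0%. The problem is systematic error that changes with depth, which is different from random scatter between women. The planned SD cannot tell the two apart, and it is not part of the decision rule.

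Two things are at stake. First, the TOST is the only formal rule in the plan that leads towards further investigation, and it could carry forward a method that under-reads deep invasion, although the Background bases the value of SFI on the depth reading. Second, the stated conclusion about the discrepancy is wider than a test of a mean signed difference can support.

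**Working it through.** **1. The plan's own figure.** Inputs from section 14c: n = 20, mean 0%, SD 37%, limits ±25%, α = 0.10 for each one-sided test. The standard error is 37/√20 = 8.27. Normal approximation: 2Φ(25/8.27 − 1.282) − 1 = 2Φ(1.74) − 1 = 0.918. Simulation of the t-based test gives 0.905. The stated power above 90% reproduces, and the largest SD that keeps 90% power at n = 20 is 37.3%. With n = 100 that SD rises to about 85%.

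**2. What a pass says about individual women.** At the planned limit (mean 0%, SD 37%, normal model), the share differing by more than 25% is 2[1 − Φ(25/37)] = 0.50. The limits of agreement are ±1.96 × 37 = ±73%. So a mean inside ±25% does not show that discrepancies are below 25%.

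**3. Cancellation within the plan's own SD.** Assume half the women have mean error +30%, half −30%, with within-group SD 15%. The overall mean is 0% and the overall SD is √(15² + 30²) = 33.5%, below 37%. The trial passes with probability 0.96 at n = 20 and 1.00 at n = 100. About 63% of women are wrong by more than 25%, since Φ((30 − 25)/15) = Φ(0.33) = 0.63.

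**4. A reader whose bias changes smoothly with depth.** If SFI = a + b × PS, the percent error at depth PS is 100(a/PS + b − 1). For a = 1.5 mm and b = 0.55 this is 150/PS − 45:

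| PS depth (mm) | 2 | 4 | 10 | 12 |
|---|---|---|---|---|
| Percent error | +30.0 | −7.5 | −30.0 | −32.5 |

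The pooled mean is 100a·E(1/PS) + 100(b − 1). The documents give no depth distribution, so four were assumed:

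| PS distribution (assumed) | E(1/PS) | 1 + 0.65 PS | 1.5 + 0.55 PS | 2 + 0.65 PS |
|---|---|---|---|---|
| Lognormal, median 4 mm, log-SD 0.5 | e^0.125/4 = 0.2833 | −6.7% | −2.5% | +21.7% |
| Lognormal, median 4 mm, log-SD 0.8 | e^0.32/4 = 0.3443 | −0.6% | +6.6% | +33.9% |
| Uniform 1–15 mm | ln(15)/14 = 0.1934 | −15.7% | −16.0% | +3.7% |
| Uniform 0.5–12 mm | ln(24)/11.5 = 0.2764 | −7.4% | −3.5% | +20.3% |

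The first two readers have a pooled mean inside ±25% in every row. The third does not.

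**5. Simulated pass rates.** n = 100, α = 0.10 per side, reading-error SD 1 mm, PS treated as error-free, SFI truncated at 0. Ranges are over the four distributions.

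| Reader | Trial passes | Deepest quarter, mean error |
|---|---|---|
| 1 + 0.65 PS | 98.6% to 100% | −21% to −27% |
| 1.5 + 0.55 PS | 88% to 100% | −24% to −34% |
| 2 + 0.65 PS | 1% to 99.8% | – |
| 2 + 0.55 PS | 19% to 100% | – |
| 3 + 0.5 PS | 0% to 92% | – |

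At n = 20 the first two readers pass between just under 40% and 87% of the time, so masking is stronger at the enrolment of 100.

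**6. Would a regression show it?** At n = 100 the 95% CI for the slope of SFI on PS excluded 1 in about 100% of trials with the first two readers, and in about 5% with an unbiased reader. A TOST confined to the deeper half is a weaker screen: it still passed in up to 94% (slope 0.65) and 84% (slope 0.55) of trials.

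**The case against.** The strongest reply is that the failure needs particular biases. Percent errors inflate in shallow tumours, so marked over-reading there pushes the pooled mean out of range and the trial fails. A reader might infer from the cancellation argument that such a method will pass. The documents do not support that: depth mix and bias are unknown, and the last three readers above can fail often. This part of the objection stands, and the point is that a biased method can pass.

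A second tempting inference is that shallow tumours carry most of the weight. The planned mean weights every woman equally. Shallow tumours dominate its variance only if reading error is constant in millimetres, which no section states. If error is proportional to depth, the percentage scale is the natural one.

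Other replies stand in part:

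- With slope 0.65 the deepest quarter averages −21% to −27%, which straddles the plan's own 25% tolerance. Slope 0.55 is the clearer example.
- The SD will be reported, and it is 31% to 68% for the first two readers. That is a warning, though a non-binding one that cannot separate scatter from trend.
- The study is a pilot, the TOST serves the secondary objective, and a pass leads only to considering more work. Section 9 keeps frozen section as routine care, so nothing here supports the inference that SFI would direct lymphadenectomy in this trial.
- The Background's criterion is the 50% point of the muscle together with grade. A regression on depth does not show whether women are classified correctly at 50%. A correlation would not expose the bias either, because a reader with slope 0.65 can correlate very highly with PS.

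**Conclusion.** The concern holds in a limited form. The decision rule in section 14c cannot see bias that changes with depth, and its stated conclusion goes beyond what the pooled mean shows. At n = 100 a reader with SFI = 1.5 mm + 0.55 × PS passes 88% to 100% of the time while the deepest quarter is under-read by 24% to 34%. A pass is possible and not assured: SFI = 2 mm + 0.65 × PS passes 1% to 99.8% of the time.

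These sizes rest on assumed depth distributions, linear bias, a 1 mm reading-error SD, error-free PS and no women with zero PS depth. The structural finding and the mismatch in the conclusion need none of these assumptions.

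A reader might also infer that a separate equivalence test in the deeper half should become a condition for going forward. The results do not support that, because such a test still passes for biased readers in up to 94% of trials.

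**What to change.** Two changes to section 14c:

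- **(a) Relate error to depth.** Add a regression of SFI depth on PS depth (or of the difference on depth), with a difference-versus-depth plot. Report intercept and slope with 95% CIs, and the predicted percent bias with its CI at the 75th percentile of PS depth. Read these alongside the TOST before deciding on further investigation. Report the mean percent difference with CI in the deeper half descriptively, without making it a gate.
- **(b) Narrow the conclusion.** State that a TOST pass shows only that the mean signed percent difference lies within ±25%, and drop the statement that the discrepancy in invasion depth is below 25%.

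The text should note that error in PS pulls the slope below 1 even for an unbiased reader. With an assumed PS error SD of 1 mm, the expected slope is var/(var + 1). For the lognormal with log-SD 0.5, var = 16·e^0.25(e^0.25 − 1) = 5.8 and the slope is 5.8/6.8 = 0.85. With log-SD 0.8, var = 16·e^0.64(e^0.64 − 1) = 27.2 and the slope is 27.2/28.2 = 0.96. A slope somewhat under 1 should therefore be judged together with the predicted percent bias.

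The cost is protocol wording and one extra analysis on paired depths already collected, with no added patients or procedures. The downside is a narrower claim from a positive test.

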7. PATIENT POPULATION

Women with documented endometrial cancer who are scheduled for a hysterectomy as part of their initial cancer staging.

Eligibility Criteria: Subjects are eligible for the study if the following inclusion and exclusion criteria are met:

Inclusion Criteria:

1. Documented endometrial cancer and scheduled for hysterectomy as part of their treatment.
2. No known allergy to fluorescein dye
3. Ability to understand and sign informed consent
4. 18 year of age or older

Exclusion Criteria:

1. Prior hysterectomy
2. Known sensitivity to fluorescein dye

8. INVESTIGATIONAL AGENT – Fluorescein dye for intravenous injection

- a. General Description:** Fluorescein is a synthetic organic compound with a dark orange color that is dissolved in water. It is supplied in a glass ampule with 500 mg of fluorescein sodium in 5 mL of water. The dye is injected intravenously and is stimulated by blue light (Woods lamp) in the range of 465 to 490 nm. Under the blue light, it will fluoresce as a bright yellow-green color.
- b. Manufacturing and Formulation:** Fluorescein 500mg/5mL is a sterile solution containing fluorescein sodium for intravenous injection. It is manufactured by multiple companies including Alcon Chemical (Fluorescite). Each 1.0 mL of solution contains 100 mg fluorescein sodium. One ampoule of 5mL contains 500 mg fluorescein sodium.
Excipients: Sodium hydroxide for pH adjustment, water for injections.
- c. Preparation:** Comes packaged as a single ampule containing 5 cc of fluorescein dye.
- d. Dosing Administration or Utilization:** One ampule (5 cc) injected intravenously prior to ligation of the uterine arteries.
- e. Storage and Disposition:** Fluorescein ampules should be stored between 5°C to 25°C.
- f. Label Information:** See Appendix I: Manufacturer's label
- g. Agent Ordering:** Fluorescein dye will be purchased by Pharmacy for this study, and the Division of Gynecologic Oncology will reimburse pharmacy as subjects complete the study.
- h. Agent Accountability:** UAMS Pharmacy Department

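### The equivalence test divides by permanent-section depth, so it cannot be calculated for cancers without invasion, and no planned analysis measures false-positive invasion by fluorescein

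*Combined protocol and SAP*

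**What the plan says.** Section 14c defines two percentage differences. The SFI-versus-PS difference is "expressed as a percentage of the PS-based invasion depth". The SFI-versus-frozen-section (FS) difference is "expressed as a percentage of the FS-based invasion depth". The plan applies them without restriction: "For each study subject, the paired difference in invasion depths determined using the SFI versus FS methods will be calculated", and likewise for PS. Each is to be summarised by mean and SD. Only the SFI–PS mean is tested, by TOST against −25% and +25% at α = 0.10, and a pass leads to considering further study of the method. The whole analysis follows a preliminary step: "Provided that it works, the analysis plan in support of the Secondary Objective is as follows". No statistic or threshold is given for that step.

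Section 7 admits women with "Documented endometrial cancer and scheduled for hysterectomy as part of their treatment" and does not ask for myometrial invasion. Section 5 discusses lymph node removal "In women with cancer that does not invade the uterine muscle" as well as in low-grade disease invading less than half the muscle, and says of SFI that "this could represent a valuable intraoperative tool to determine which patients require lymphadenectomy".

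The only data-handling rule is Section 14d: "Missing data will be treated as missing, and will not be imputed". The rest of that section deals with spurious values.

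**The concern.** A PS depth of zero is a valid reading that the trial should expect. It is neither missing nor spurious, so 14d does not apply. As written, 14c requires a division by zero for these women. Whoever runs the analysis must invent a rule after seeing the data.

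The easiest rule is to drop them. The test set would then be chosen by the reference result, and SFI>0 with PS=0 would leave no trace in the test. No other planned analysis picks it up. The SFI–FS summary is untested, is not a comparison with the reference standard, and fails in the same way at FS=0. The preliminary step has no criterion. The accuracy comparison shown in the Section 4 schema has no statistic attached.

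Invaded versus not invaded is part of the decision for which Section 5 proposes SFI. A positive TOST would speak only for women with PS>0, yet 14c would read it as general agreement.

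**Working it through.** **Inputs from Section 14.** Limits ±25%; α = 0.10 for each one-sided test; true mean 0%; SD 37%; 20 subjects in the power statement; 100 to be enrolled. **Assumption:** 10% to 40% of subjects have PS=0, since the documents give no rate.

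**1. The plan's own figure.** The TOST passes when |mean| + t(0.90, n−1) × s/√n < 25. Integrating over the distribution of s with n = 20, SD 37 and mean 0 gives power 0.906; 1,000,000 simulations give 0.905. The normal approximation is 2Φ(25√20/37 − 1.282) − 1 = 2Φ(1.740) − 1 = 0.918. The stated power above 90% therefore reproduces, but it presumes that every subject's percentage exists.

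**2. The metric at zero.** The quantity is 100 × (SFI − PS)/PS. At PS=0 it is 0/0 if SFI=0 and infinite if SFI>0. The chance of at least one such woman among n is 1 − (1 − p)^n. With p = 5%, lower than the range used below, this is 1 − 0.95^100 = 99.4% for 100 subjects.

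**3. If PS=0 women are dropped** (100 enrolled, SD 37%, mean 0):

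| Share with PS=0 | Outside the ratio | Evaluable | TOST power | Misread if SFI shows invasion in none / half / all of them |
|---|---|---|---|---|
| 10% | 10 | 90 | >0.9999 | 0 / 5 / 10 |
| 20% | 20 | 80 | >0.9999 | 0 / 10 / 20 |
| 30% | 30 | 70 | >0.9999 | 0 / 15 / 30 |
| 40% | 40 | 60 | 0.9999 | 0 / 20 / 40 |

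Simulation (20,000 runs per cell; 10, 30 or 40 women with PS=0; false-positive rate 0, 0.5 or 1) gave a pass rate of 0.9999 to 1.0000 in every cell. This follows by construction, because readings outside the test set cannot alter the test.

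**4. What the test does see.** Over-reading at PS>0 enters the mean. Missed invasion also enters: SFI=0 at PS>0 scores 100 × (0 − PS)/PS = −100%. The blind spot is confined to PS=0.

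**5. Power.** Power falls materially only if 20 women are enrolled. Losing 40% of them leaves n = 12 and power 0.667. With 100 enrolled, power is not an issue.

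**6. Shallow depths (secondary).** Small PS values inflate the ratio. The assumed model is PS uniform up to 15 mm, SFI = max(PS + error, 0), error SD 2 mm, 70 evaluable, 40,000 runs. For a shallowest depth of 0.5, 1 or 2 mm, the SD of the percentage is 59%, 45% or 35%, and the TOST passes in 90%, 99% or >99.9% of runs. Without truncating SFI at zero, the SDs are 73%, 52% and 37%, and the pass rates 85%, 98% and >99.9%. In this model shallow depths alone do not reverse the decision.

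**7. What a specificity estimate could show.** With no false positives among m women with PS=0, the exact two-sided 95% upper limit on the false-positive rate is 1 − 0.025^(1/m). For m = 10, 20, 30 and 40 this is 30.8%, 16.8%, 11.6% and 8.8%.

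**The case against.** This is a single-arm pilot. A pass leads only to considering further work, and frozen section remains routine care, so no current patient is at risk. Followed literally, the formula fails visibly at the first PS=0 woman and forces a decision; silent exclusion is an assumption. All three depths are recorded, so a rule could be added before analysis without losing data. Section 5 also treats low-grade cancer invading less than half the muscle like non-invasive cancer, so a falsely shallow reading in low-grade disease need not cross the boundary described there.

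Much of this stands. The harm is a wrong go/no-go decision, the exclusion default and the PS=0 range are assumptions, and the counts of misread women are not split by grade. An invasion yes/no table also does not address the 50% depth. None of this supplies the missing rule. A visible failure still means choosing the rule after the data are known, and the TOST is the pilot's only formal decision step.

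**Conclusion.** The concern holds and must be fixed before analysis. The planned metric is undefined on data that the eligibility criteria admit and the Background foresees, no rule resolves it, and no planned statistic measures SFI reading invasion where PS shows none. If PS=0 women are dropped, and if they make up 10% to 40% of 100 subjects, between 10 and 40 women leave the test. Up to all of them could be misread while the pass probability stays at 0.9999 or above. That figure rests on the plan's SD of 37% and a true mean of 0 among women with PS>0. The undefined ratio itself rests on no assumed rate.

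**What to change.** Amend Section 14c to state that:

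1. The percentage TOST applies to subjects with PS>0 and its conclusion is limited to them; likewise FS>0 for the SFI–FS summary.
2. The number of subjects with PS=0 is reported.
3. All subjects with SFI and PS readings enter a 2×2 table of invasion yes/no, SFI against PS, with sensitivity, specificity and exact 95% confidence intervals. The table is read alongside the TOST before any decision on further investigation.
4. The signed SFI − PS difference in the recorded unit is summarised descriptively for everyone, including PS=0.

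The ±25% limits stay. No new measurement is needed, because the three depths are already the endpoints in 14b. The costs are a little more analysis, an equivalence claim confined to invasive cancers, and an imprecise specificity if few women have PS=0.
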